9.4 Renal safety monitoring

Every renal laboratory trigger or renal event must be followed up by the investigator or designated personnel at the trial site. Recommended follow-up assessments are listed in [Appendix 2](#).

All follow-up information, and the procedures performed must be recorded as appropriate in the CRF. Refer to the Site Operations Manual for additional details.

9.5 Reporting of study treatment errors including misuse/abuse

Medication errors are unintentional errors in the prescribing, dispensing, administration or monitoring of a medicine while under the control of a healthcare professional, patient/subject or consumer (EMA definition).

Misuse refers to situations where the medicinal product is intentionally and inappropriately used not in accordance with the protocol.

Abuse corresponds to the persistent or sporadic, intentional excessive use of a medicinal product, which is accompanied by harmful physical or psychological effects.

All study treatment errors and uses outside of what is foreseen in the protocol will be collected in the dose administration record (DAR) CRF. Study treatment errors are only to be reported to Chief Medical Office and Patient Safety (CMO& PS) department if the treatment error is associated with an SAE.

All instances of misuse or abuse must be documented in the adverse event (AE) CRF irrespective of the misuse/abuse being associated with an AE/SAE. In addition, all instances of misuse or abuse must be reported to Novartis Chief Medical Office and Patient Safety (CMO& PS). As such, instances of misuse or abuse are also to be reported using the SAE form/CRF. [Table 9-1](#) summarizes the reporting requirements.

Table 9-1 Guidance for capturing study treatment errors

Treatment error type	Document in Dose Administration (DAR) CRF	Document in AE CRF	Complete SAE form/CRF
Unintentional study treatment error	Yes	Only if associated with an AE	Only if associated with an SAE
Misuse/Abuse	Yes	Yes	Yes, even if not associated with a SAE

For more information on AE and SAE definition and reporting requirements, please see [Section 9.1](#) and [Section 9.2](#), respectively.

9.6 Pregnancy reporting

To ensure subject safety, each pregnancy occurring after signing the informed consent must be **reported to Novartis within 24 hours** of learning of its occurrence. The pregnancy should be followed up to determine outcome, including spontaneous or voluntary termination, details of the birth, and the presence or absence of any birth defects, congenital abnormalities, or maternal and/or newborn complications.

Pregnancy must be recorded on the Pharmacovigilance Pregnancy Form and reported by the investigator to the local Novartis Chief Medical Office and Patient Safety (CMO& PS) Department. Pregnancy follow-up should be recorded on the same form and should include an assessment of the possible relationship to the study treatment.

Any SAE experienced during the pregnancy and unrelated to the pregnancy must be reported on a SAE form.

The study drug must be discontinued*, though the subject may stay in the study, if she wishes to do so. All assessments that are considered as a risk during pregnancy must not be performed. The subject may continue all other protocol assessments.

9.7 Prospective suicidality assessment

The Columbia-Suicide Severity Rating Scale (C-SSRS), is a questionnaire that prospectively assesses Suicidal Ideation and Suicidal Behavior. The C-SSRS must be administered at each visit, including unscheduled visits.

The C-SSRS, which uses a semi-structured interview to probe subject responses, will be administered by an individual who has received training and certification in its administration. At the first study visit, the “baseline/screening” version of the C-SSRS, will be administered. This version assesses Suicidal Ideation and Suicidal Behavior during the subject’s lifetime and during a predefined period. At subsequent visits, the “since last visit” version will be administered.

If, at any time after screening and/or baseline, the score is “yes” on item 4 or item 5 of the Suicidal Ideation section of the C-SSRS or “yes” on any item of the Suicidal Behavior section, the subject must be referred to a mental health care professional for further assessment and/or treatment. The decision on whether the study treatment should be discontinued is to be taken by the investigator in consultation with the mental health professional to whom the subject is referred.

In addition, all life-threatening events must be reported as SAEs. For example, if a subject answers “yes” to one of the questions in the Suicidal Behavior section, an SAE must be reported if the event was life-threatening. All events of “Non-Suicidal Self-Injurious Behavior” (question also included in the Suicidal Behavior section) should be reported as AEs and assigned the appropriate severity grade.

All SAEs relating to suicidal behavior must be reviewed by the Safety Management Team or Early Project Teams.

9.8 Early phase safety monitoring

The Investigator will monitor adverse events in an ongoing manner and inform the Sponsor of any clinically relevant observations. Any required safety reviews will be made jointly between medically qualified personnel representing the Sponsor and Investigator. Such evaluations may occur verbally, but the outcome and key discussion points will be summarized in writing (e-mail) and made available to both Sponsor and all Investigator(s). Criteria pertaining to stopping the study/treatment or adapting the study design are presented above.

When two or more clinical site(s) are participating in the clinical study, the Sponsor will advise the Investigator(s) at all sites in writing (e-mail) (and by telephone if possible) of any new, clinically relevant safety information reported from another site during the conduct of the study in a timely manner.

10 Data review and database management

10.1 Site monitoring

Before study initiation, at a site initiation visit or at an investigator's meeting, a Novartis representative will review the protocol and data capture requirements (eCRFs) with the investigators and their staff. During the study Novartis employs several methods of ensuring protocol and GCP compliance and the quality/integrity of the sites' data. The monitor will visit the site to check the completeness of subject records, the accuracy of data capture / data entry, the adherence to the protocol and to Good Clinical Practice, the progress of enrollment, and ensure that study drug is being stored, dispensed, and accounted for according to specifications. Key study personnel must be available to assist the monitor during these visits.

Continuous remote monitoring of each site's data may be performed by Novartis or CRO working on behalf of Novartis. Additionally, a central analytics organization may analyze data and identify risks & trends for site operational parameters, and provide reports to Novartis Clinical Teams to assist with trial oversight.

The investigator must maintain source documents for each subject in the study, consisting of case and visit notes (hospital or clinic medical records) containing demographic and medical information, laboratory data, electrocardiograms, and the results of any other tests or assessments. All information on CRFs must be traceable to these source documents in the subject's file. The investigator must also keep the original informed consent form signed by the subject (a signed copy is given to the subject).

The investigator must give the monitor access to all relevant source documents to confirm their consistency with the data capture and/or data entry. Novartis monitoring standards require full verification for the presence of informed consent, adherence to the inclusion/exclusion criteria, documentation of SAEs, and the recording of data that will be used for all primary and safety variables. Additional checks of the consistency of the source data with the CRFs are performed according to the study-specific monitoring plan. No information in source documents about the identity of the subjects will be disclosed.

10.2 Data collection

Designated investigator staff will enter the data required by the protocol into the Electronic Case Report Forms using fully validated software that conforms to 21 CFR Part 11 requirements. Designated investigator site staff will not be given access to the EDC system until they have been trained. Automatic validation programs check for data discrepancies and, by generating appropriate error messages, allow the data to be confirmed or corrected before transfer of the data to the CRO working on behalf of Novartis. The Investigator must certify that the data entered into the Electronic Case Report Forms are complete and accurate. After database lock, the investigator will receive copies of the subject data for archiving at the investigational site.

Certain data may be captured via other source documentation (such as safety laboratory data report) and then transcribed, uploaded or transferred into the EDC system. This, and any additional data treated in this manner, will be source data verified by the study monitor per the monitoring plan and the location of source data (i.e., Source, paper or a local electronic system) will be documented prior to study start in the Data Handling Plan.

Automatic validation programs check for data discrepancies and, by generating appropriate error messages, allow the data to be confirmed or corrected before transfer of the data to the vendor working on behalf of Novartis.

Remote monitoring of the original electronic source records will take place, however on-site monitoring inspections will continue to take place in order to review data entry of source documentation directly captured on paper and transcribed into the system, to ensure protocol adherence, to assess site operational capabilities, and to perform other monitoring activities that cannot be performed remotely.

The investigator must certify that the data entered into CRFs are complete and accurate. After database lock, the investigator will receive copies of the patient data for archiving at the investigational site.

Data not requiring a separate written record will be defined in the Site Operations Manual and [Assessment schedule \(Section 8.1\)](#) and can be recorded directly on the CRFs. All other data captured for this study will have an external originating source (either written or electronic) with the CRF not being considered as source.

All data should be recorded, handled and stored in a way that allows its accurate reporting, interpretation and verification.

10.3 Database management and quality control

CRO working on behalf of Novartis review the data entered into the CRFs by investigational staff for completeness and accuracy and instruct the site personnel to make any required corrections or additions. Queries are sent to the investigational site using an electronic data query. Designated investigator site staff is required to respond to the query and confirm or correct the data. If the electronic query system is not used, a paper Data Query Form will be faxed to the site. Site personnel will complete and sign the faxed copy and fax it back to CRO working on behalf of Novartis who will make the correction to the database. The signed copy of the Data Query Form is kept at the investigator site.

Concomitant medications entered into the database will be coded using the WHO Drug Reference List, which employs the Anatomical Therapeutic Chemical classification system. Medical history/current medical conditions and adverse events will be coded using the Medical dictionary for regulatory activities (MedDRA) terminology.

Laboratory samples will be processed centrally and the results will be sent electronically to Novartis (or a designated CRO).

At the conclusion of the study, the occurrence of any emergency code breaks will be determined after return of all code break reports and unused drug supplies to Novartis.

The occurrence of relevant protocol deviations will be determined. After these actions have been completed and the database has been declared to be complete and accurate, it will be locked and the treatment codes will be unblinded and made available for data analysis. Any changes to the database after that time can only be made after written agreement by Novartis management.

Commercially Confidential Information

10.4 Data Monitoring Committee

Not applicable.

10.5 Adjudication Committee

Not applicable.

11 Data analysis

The analysis will be conducted on all subject data at the time the trial ends. Any data analysis carried out independently by the investigator should be submitted to Novartis before publication or presentation.

11.1 Analysis sets

For all analysis sets, subjects will be analyzed according to the study treatment received.

The safety analysis set will include all subjects that received any study drug.

The PK analysis set will include all subjects with at least one available valid (i.e. not flagged for exclusion) PK concentration measurement, who received any study drug and with no protocol deviations that impact on PK data.

The PD analysis set will include all subjects with available PD data and no protocol deviations with relevant impact on PD data.

11.2 Subject demographics and other baseline characteristics

All data for background and demographic variables will be listed by treatment group and subject. Summary statistics will be provided by treatment group.

Relevant medical history, current medical conditions, results of laboratory screens, drug tests and any other relevant information will be listed by treatment group and subject.

11.3 Treatments

Data for study drug administration (rescue medication) and concomitant therapies will be listed by treatment group and subject.

11.4 Analysis of the primary variable(s)

The primary objective is to evaluate the effect of AFQ056 in reducing cocaine use.

11.4.1 Primary Variable(s)

The primary variable is the proportion of cocaine use days during the treatment period (days 1-98).

For each patient, the proportion of cocaine use days will be calculated by dividing the number of days of cocaine use during the treatment period, i.e. 98 days for completers and number of days between Day 1 and day of last dose in case of premature discontinuation of study treatment. It is considered as a continuous variable with a normal distribution. The cocaine consumption will be recorded daily (Yes/No) using the TLFB during the entire study.

11.4.2 Statistical model, hypothesis, and method of analysis

A Bayesian analysis will be conducted on the proportion of cocaine use days

Commercially Confidential Information

11.4.3 Handling of missing values/censoring/discontinuations

In case of premature discontinuation of study treatment, the calculation of the primary variable will be done on the period with both TLFB data available and study treatment was taken. No missing data is expected between visits per the TLFB completion guidelines and investigator's checks at the visits.

For sensitivity analysis, the incomplete profiles will be included in longitudinal analyses.

11.4.4 Sensitivity analyses

Sensitivity analyses will be performed using other models if the distribution of the data is not deemed normal.

Additionally, the profiles of consumption over time will be compared between treatment groups through analyses of longitudinal data (weekly use and monthly use) using linear mixed models for repeated measures or other models depending on the distribution.

Data visualization techniques will be used in order to detect potential patterns in the daily data obtained from the TLFB.

The missing data mechanism will be explored to check that the missing data due to dropouts are at least missing at random.

11.5 Analysis of secondary variable(s)

The secondary objectives are to assess the effect of AFQ056 on other measures of cocaine use and on measures of alcohol use, to assess the safety and tolerability and to evaluate the PK of AFQ056.

11.5.1 Efficacy / Pharmacodynamics

11.5.1.1 Measure of cocaine in (BE) in urine

Two urine samples per week will provide a quantitative measure of cocaine's metabolite BE. The proportions of positive urine samples over the treatment period will be compared between groups using a t-test.

The quantitative BE profiles over time will be explored using visualization techniques and compared between groups using models appropriate to the distribution of the data.

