2.3 Exploratory objective(s)

Commercially Confidential Information

from cocaine use. For all examinations to be done at baseline, refer to the [Assessment schedule](#).

Treatment (days 1-98): following baseline, on Day 1, approximately 60 eligible patients will be randomly assigned in a 1:1 ratio to either AFQ056 or placebo

- Group A - AFQ056: up-titration regimen for the first 2 weeks (14 days): 50 mg bid from Day 1 to Day 7 , 100 mg bid from Day 8 to Day 14 , followed by dosing at 200 mg bid for 84-days
- Group B: matching placebo.

Study drug: must be taken twice daily (bid) in the morning and evening (separated by approximately 12 hour intervals) with food. For all ambulatory morning visits that involve any study assessments or PK/urine sample collection, study medication will be self-administered by patient at study center and supervised by study personnel. On these days, standard breakfast should be served at study center and consumed by the patient during his/her medication intake.

During treatment period, patients will also undergo assessments with various scales and questionnaires, as well as safety assessments and pharmacokinetic sampling at pre- and 2 ± 1 -hour post dose per SoA. For a detailed outline of all study assessments and time points refer to the [Assessment schedule](#).

Urine samples (days1-113): samples will be collected at study center twice per week, with at least 48 hours separating tests. The sample collection will be assayed quantitatively for the presence of cocaine's metabolite (benzoylecgonine (BE)), as well as, other illicit drugs may be assayed. It is expected that a total of approximately 33 urine samples will be collected during study conduct: 28 samples from patients who remain in treatment for the 14 weeks (total of 4 samples: weeks 1–2 of up-titrations); 24 samples in weeks 3–14 (maintenance dose); 4 samples in weeks 15–16 (follow up) and finally 1 last sample at end of study visit. If a patient fails to attend the clinic or refuses to provide a sample on a scheduled testing day, samples will be considered positive unless an excused absence is granted (e.g.. illness, other personal reason). In cases of missed or refused samples, samples should be collected on the next day whenever possible.

Clinical support to ensure medication and protocol's adherence:

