4.1 Inclusion criteria

CUD patients eligible for inclusion in this study must fulfill **all** of the following criteria:

1. Understand the study procedures and provide written informed consent before any assessment is performed.
2. Male and female subjects, 18 to 65 years of age (inclusive) and diagnosed with Cocaine Use Disorder according to DSM 5 (Diagnostic and Statistical Manual of Mental Disorders, 5th Ed.).
3. Must use cocaine through snorting (intranasally), as primary route of administration.

4. Recent cocaine use confirmed by positive urine screen for 1 or more benzoylecgonine (BE).
5. Must be seeking treatment for cocaine dependence and have a desire to reduce or cease cocaine use as per goals assessed at baseline.
6. Must be abstinent from cocaine use for at least 3 days preceding 1st dosing (Day 1) as assessed by self-report TLFB. The two urine drug screen samples at v2 and v3 must show a decrease in BE level or both must be negative.
7. Must be in good health as determined by medical history, physical examination, at screening.
8. At screening and baseline, vital signs (systolic and diastolic blood pressure and pulse rate) must be within the acceptable ranges by the investigator considering the cocaine's increasing effect on pulse rate in order for the subject to qualify. The investigator may be guided to use the below ranges:
 - systolic blood pressure, 90-150 mmHg
 - diastolic blood pressure, 50-90 mmHgThree readings are acceptable. At least the one of three readings must be within the acceptable ranges.
9. Patients must be able to:
 - communicate well verbally with the Investigator and to understand written instructions.
 - verbalize a willingness to complete all study procedures.
 - verbally acknowledge that she/he will be able to attend each scheduled visit, and that she/he does not have any already scheduled events or activities that may substantially interfere with study participation.

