8.8.3 Positive Reinforcement (PR)

For each study visit patients will receive money compensation for travel expenses. In order to stimulate clinic attendance and to enable optimal monitoring of patients' medication adherence and health (including adverse events), patients will be remunerated for complying with study visits and standard requirements (urine submission, TLFB, medication diary, adverse events, and basic physical examination). In order to reinforce regular participation with study assessments a bonus will be provided each time patients attend two consecutive study visits. Finally, patients will receive additional remuneration for their time investment in case of ECG-evaluations and for extended study visits with additional questionnaires and/or PK-blood sampling. The maximum remuneration for patients complying with all study assessments. Given our experience with pharmacotherapy studies with cocaine dependent patients, we expect that patients, on average, will attend a maximum of 70-80% of all planned study visits.

In addition to positive reinforcement, participants will be stimulated at every planned visit and encouraged for attending appointments, as well as adherence to the protocol.

Positive Reinforcement will be made available for the sites as a separate document.

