11.5.1.2 Measures of alcohol use

Alcohol consumption will be recorded by the patients using TLFB. The number of standard drinks will be recorded daily.

The proportion of days of alcohol consumption during the study treatment period will be compared between groups using an ANCOVA model with treatment as factor and past alcohol consumption as covariate.

The longitudinal profiles (daily number of drinks, weekly and monthly mean number of drinks) will be explored.

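### Protocol 11.5.1.1 compares the proportion of positive urine samples with an unadjusted t-test; adjusting for pre-treatment cocaine use already collected would narrow the interval at almost no cost

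*Protocol*

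**What the plan says.** Protocol 11.5.1.1 gives the analysis in one sentence: "The proportions of positive urine samples over the treatment period will be compared between groups using a t-test". It names no covariate. It then adds a comparison of quantitative benzoylecgonine (BE) profiles, with the model left open.

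The covariate data exist. Table 8-1 marks TLFB cocaine from screening, and Protocol 11.4.1 says: "The cocaine consumption will be recorded daily (Yes/No) using the TLFB during the entire study". Entry depends on it too (Protocol 4.1, item 6): "Must be abstinent from cocaine use for at least 3 days preceding 1st dosing (Day 1) as assessed by self-report TLFB". The same item constrains early urine results: "The two urine drug screen samples at v2 and v3 must show a decrease in BE level or both must be negative".

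The neighbouring alcohol endpoint (Protocol 11.5.1.2) is analysed "using an ANCOVA model with treatment as factor and past alcohol consumption as covariate".

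On missed visits, the study-design text on urine samples (printed after the redacted part of Section 2.3) says that if a patient does not attend or refuses, "samples will be considered positive unless an excused absence is granted". It adds: "In cases of missed or refused samples, samples should be collected on the next day whenever possible". Protocol 8.8.3 expects that "patients, on average, will attend a maximum of 70-80% of all planned study visits". Section 11.5.1.1 does not repeat the missed-sample rule, so its use in this proportion is inferred.

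Protocol 11.8 plans no power for secondary variables. SAP 6.2.3, which holds the secondary models, is redacted.

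**The concern.** Of the efficacy endpoints listed under the primary and secondary objectives, urine BE is the only biological check on self-reported cocaine use. With about 30 patients per arm its between-group comparison will be imprecise. If use before treatment predicts use during treatment, a test that ignores it leaves explainable variation in the error term. The protocol already adjusts the alcohol endpoint this way and gives no reason for treating the cocaine urine endpoint differently.

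A second, smaller matter is interpretation. With 28 scheduled on-treatment samples and attendance of 70-80%, about 28 × 0.20 = 5.6 to 28 × 0.30 = 8.4 samples per completer could be scored positive without a result, before excused absences and next-day collection. The readable text shows no version of this proportion based on observed samples alone.

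**Working it through.** **Inputs.** From the documents: 30 per arm and a standard deviation (SD) of 32 points (Protocol 11.7); 28 on-treatment samples; attendance of 70-80%. The SD belongs to the TLFB proportion of use days and is borrowed here. Assumed: two-sided 5% level, a 20-point difference, and correlation r between pre-treatment TLFB use and the on-treatment urine proportion. The documents do not give r, so a range is shown. The plan states no precision or power for this endpoint, so there is no planned figure to reproduce.

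**Unadjusted t-test.** SE = 32 × √(2/30) = 8.26 points. Half-width = t(58 df) × SE = 2.002 × 8.26 = 16.5. Power for 20 points (noncentral t) = 66%.

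**ANCOVA.** SE is multiplied by √(1 − r²), with 57 df. The equivalent unadjusted sample size is 30/(1 − r²).

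| r | SE | Half-width | Power | Equivalent n per arm |
|---|---|---|---|---|
| 0 | 8.26 | 16.5 | 66% | 30 |
| 0.3 | 7.88 | 15.8 | 70% | 33 |
| 0.5 | 7.16 | 14.3 | 78% | 40 |
| 0.7 | 5.90 | 11.8 | 91% | 59 |

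At r = 0, allowing also for chance covariate imbalance, power is about 65.5% against 66.3%. In simulation, with proportions confined to 0-1, both tests kept type I error at 4.5-5.1%.

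**Missed samples scored positive.** If misses are unrelated to use and none is excused or recovered, a true rate p becomes a·p + (1 − a) at attendance a, so a difference is multiplied by a: 20 × 0.70 = 14 and 20 × 0.80 = 16 points. If half the misses are excused and leave the denominator, the factor is a/[a + (1 − a)/2], giving 20 × 0.70/0.85 = 16.5 and 20 × 0.80/0.90 = 17.8.

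**Do the two versions bracket the truth?** Take 50% against 30% positive, with miss probabilities of 0.40 on positive and 0.10 on negative samples in both arms. Missed = positive gives 0.50 + 0.50 × 0.10 = 0.55 and 0.30 + 0.70 × 0.10 = 0.37, a difference of 18.0. Simulating patients with beta-distributed rates (SD 0.32, 28 samples), observed-only gives about 18.2 to 18.3. Both lie below the true 20.

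**Can observed-only overstate?** Take 40% against 60% positive, with misses only on would-be positives. Holding attendance equal across arms at 70-80%, simulation gives observed-only differences of about 23-28 points. Equal attendance forces positives to be missed more often in the lower-use arm: at 70% attendance, 0.30/0.40 = 75% against 0.30/0.60 = 50%. With a common miss probability of 0.5 at the same rates, observed-only gives about 19.5 and the inflation disappears.

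**The case against.** The strongest reply is that nothing here is an error. Randomisation makes the t-test valid, the endpoint is secondary, and no power is claimed for it. That stands, and it is why the priority is modest.

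Second, the precision gain rests on a borrowed SD and an assumed correlation; at r = 0.3 it is only four power points. That also stands. But the cost at r = 0 is negligible, so adjustment does not need the correlation to be known.

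Third, a reader might infer that the final analysis ignores baseline use. The documents do not support that. SAP 6.2.3 is redacted, and SAP 6.2.2 refers to a model there with a country effect. That mention is in the alcohol paragraph, so it does not settle the urine analysis either way.

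Fourth, a reader might conclude that the missed-sample rule is biased and that observed samples would give the right answer. Which version is nearer the truth depends on why samples are missed, which cannot be known in advance. The rule is softened by excused absences, next-day collection and payment for attendance. The quantitative BE comparison, averaged weekly in SAP 6.2.2 from samples obtained, and the daily TLFB primary endpoint also help separate use from attendance. Nothing in the documents suggests that attendance will differ between arms.

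**Conclusion.** The protocol's t-test is valid but gives up precision that data already collected could supply. Under the borrowed SD of 32 points, 30 per arm and an assumed 20-point effect, adjustment shortens the interval half-width by 0.7, 2.2 or 4.7 points (16.5 less 15.8, 14.3 or 11.8) at correlations 0.3, 0.5 and 0.7. At zero correlation it costs one degree of freedom and under one point of power.

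The missed-sample issue supports an optional sensitivity analysis and no more. The shrinkage to 14-16 points is a worst case that assumes misses unrelated to use, none excused and none recovered. It is tempting to present the two versions as limits around the true effect; the example above, with both near 18 against 20, shows that this can fail.

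The conclusion applies to the wording of Protocol 11.5.1.1, not to the redacted SAP model.

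**What to change.** In Protocol 11.5.1.1, replace the t-test with ANCOVA on the proportion of positive samples, with treatment as factor and the pre-treatment TLFB proportion of cocaine-use days as covariate. Fix the covariate window in advance and end it before the three abstinent days required by inclusion criterion 6: those days are zero for every eligible patient and carry no information. TLFB use is preferable to baseline BE because the same criterion constrains the results at visits 2 and 3. If SAP 6.2.3 already adjusts, align the protocol text with it.

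Optional: keep missed = positive, report an observed-samples version as a sensitivity analysis, and tabulate attended, recovered, excused and imputed samples by arm. Do not describe the two versions as a range containing the true effect. It would also help to say in 11.5.1.1 that the missed-sample rule applies, whether excused samples leave the denominator, and that the treatment period is that of Protocol 11.4.1.

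The cost is revised wording and one or two tables. No new data are needed. Patients with no observed sample drop out of the sensitivity analysis.
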